6.5 Archiving of documents

The investigator will keep the subject's files and original data according to the local methods and facilities. The investigator should maintain the trial documents as specified in the ICH-GCP-Guideline for 10 years. The investigator/institution should take measures to prevent accidental or premature destruction of these documents.

6.6 Funding

TRAUMOX2 is initiated by a research group of medical doctors in "Afdeling for Bedøvelse, Operation og TraumeCenter 6011, HovedOrtoCentret, Rigshospitalet, Copenhagen, Denmark". It is funded by the Novo Nordisk Foundation which is a non-profit organisation. The duration of the funding is 4 years and the amount granted is 6.326.084 DKK. It covers the sponsor's and coordinating investigator's salary, the overhead and completion costs, including that each participating centre will receive 150 euro per trial participant included with completely documented trial participants (after 30 days). Each centre will distribute the amount as agreed upon within the local organization. The Novo Nordisk Foundation is not involved in the management of the study itself, or the decision to submit the manuscript for publication, but will be mentioned in all public communication, and any publication resulting from the project will be mentioned as *"The work presented in this article is supported by Novo Nordisk Foundation grant NNF200C0063985"*. The funding will be paid to a bank account within the department in the sponsor's name. The sponsor and coordinating investigator have no conflicts of interests in relation to the Novo Nordisk Foundation. In addition, the study is also partly funded by The Lundbeck Foundation as a personal grant of 350.000 DKK to study coordinator [name]. Some of this grant will be spent on salary to [name] as well as unexpected expenses to the trial. Drug expenses will be covered by the participating centres' departmental budget. Drug expenses beyond the normal department budget will also be covered by the participating centres.

The international ATLS (Advanced Trauma Life Support) guidelines recommend that all severely injured trauma patients receive supplemental oxygen¹ based on very limited evidence.^{2,3} Thus, supplemental oxygen is commonly used in trauma patients⁴⁻¹², although it may lead to hyperoxaemia which has been associated with pulmonary complications and increased mortality.^{13,14} The TRAUMOX2 trial¹⁵ randomises adult patients with suspected major trauma to eight hours of a restrictive or liberal oxygen strategy and explores differences in mortality and pulmonary complications. This sub-study of the TRAUMOX2 trial explores whether biomarkers may explain the development of such complications.

Several mechanisms may explain why excessive oxygen administration may be harmful, such as upregulation of oxidative stress and the formation of resorption atelectases.^{16,17} Under normal physiological conditions, reactive oxygen species (ROS) are essential factors in cellular signalling and normal metabolism.¹⁸ However, during pathological situations, when the formation of ROS is excessive and the normal antioxidant defence is insufficient, there is an imbalance favouring ROS. This is called oxidative stress which is believed to result in cell injury and cell death.¹⁹ The oxidative stress in relation to supplemental oxygen is thought to be mediated through a hyperoxia-induced formation of ROS.^{20,21} A prolonged exposure to hyperoxia may play a key role in the inflammatory response, destruction of the alveolar-capillary barrier, impaired gas exchange, and pulmonary oedema.²² ROS are very volatile molecules. Therefore, biomarkers such as antioxidants, DNA/RNA damage, lipid peroxidation and protein oxidation are indirect measures of the level of oxidative stress. This is explained in more detail in the protocol amendment on biomarkers of oxidative stress to the TRAUMOX2 trial.²³

In this sub-study of the TRAUMOX2 trial, we aim to analyse biomarkers of oxidative stress that may relate to the pathophysiology of possible complications related to hyperoxaemia. We will include patients allocated to either a liberal or restrictive oxygen treatment in the TRAUMOX2 trial at the Copenhagen study site.¹⁵ The primary outcome will be the level of the biomarker malondialdehyde (MDA) at the 24-hour mark after randomisation in the TRAUMOX2 trial since MDA has previously been used as a biomarker for oxidative stress in patients and animals.²⁴⁻²⁶ This document presents the statistical analysis plan of the current sub-study of the TRAUMOX2 trial.

2. Methods

This statistical analysis plan of the sub-study on biomarkers of oxidative stress in the TRAUMOX2 trial has been written according to the *Guidelines for the Content of Statistical Analysis Plans in Clinical Trials*.²⁷ It aims to give an overview and justification of the chosen variables and statistical methods used. The database system used for this trial is REDCap.²⁸ The plan is prepared while the trial is still including patients and thus before the database is exported for analysis by the trial statistician. All analyses of the primary, secondary and exploratory secondary outcomes will be conducted according to this publication. The steering committee of the study approved this statistical analysis plan on the 5th of September 2023.

This sub-study of the TRAUMOX2 trial is part of the approval for the TRAUMOX2 trial and has been approved by the Danish Research Ethics Committee (H-21018062), the Danish Medicines Agency (EudraCT 2021-000556-19) and the Knowledge Centre on Data Protection Compliance, Health Science and Innovation in the Capital Region of Denmark.

2.1 Trial design

The biomarker sub-study is a prospective, single centre study on trauma patients at Rigshospitalet, Copenhagen, Denmark. The patients will be assessed for eligibility for this study once they are included in the international, multicentre, parallel-group, superiority, outcome assessor- and analyst-blinded, randomised, controlled trial TRAUMOX2. Therefore, it is mandatory that the included patients undergo the full intervention of either the liberal or restrictive oxygen strategy in TRAUMOX2 since data in this study depends on the entire TRAUMOX2 intervention.

2.2 Randomisation and blinding

Patients are randomised 1:1 in variable block sizes of four, six and eight, stratified by including base (prehospital base or trauma centre) and tracheal intubation (yes/no) at inclusion to either a liberal oxygen strategy (control) or restrictive oxygen strategy (intervention). The restrictive group receives the lowest dosage of oxygen ($\geq 21\%$) that ensures an SpO₂ of 94%. The liberal group receives 12-15 L O₂/min or FiO₂ = 0.6-1.0. The randomisation table was generated outside of REDCap by a statistician otherwise not affiliated with the study. The allocation sequence list and specific block size are only known by this statistician and will remain concealed from the investigators. Prior to randomisation, consent is obtained either by proxy (from another physician) or otherwise according to national legislation. Immediately afterwards, randomisation is done by opening an envelope with information on allocation. Each envelope contains a study ID that matches a study ID on the randomisation list generated by the statistician. Subsequently, informed consent is confirmed from the patient or a relative in case the patient cannot give consent. A more detailed description of the interventions and consent procedure is presented in the protocol of the TRAUMOX2 trial, the protocol of the TRAUMOX2 biomarkers of oxidative stress, and on the study website.^{15,23,29}

The treating staff will be aware of the patients' randomisation group, and due to the nature of oxygen treatment, patients and relatives will often be aware of the allocated oxygen strategy as well. While the trial is including patients for the sub-study, members of the research team will also be aware of the patients' oxygen allocation strategy.

2.3 Sample size calculation

In a study by Forsberg et al.³⁰, patients were treated with THRIVE (Optiflow to 70 L min⁻¹ of 100 % oxygen when apnoea occurred) and MDA levels were measured before and after the intervention. The MDA levels before THRIVE were 11.2 µM (SD 3.1) and after THRIVE were 12.7 µM (SD 3.1). Assuming these two time points represent the restrictive (before THRIVE) and liberal group (after THRIVE) in the TRAUMOX2 trial, we aim to detect a difference of 2 µM in MDA level between the restrictive group and the liberal group at H24. We assume that the standard deviation (SD) will be approximately 3 µM. With an estimated number of 120 trial participants, we will have at least 90% power to detect this difference at the 5% significance level and a drop-out rate of 5%. However, the number of patients will depend on the TRAUMOX2 study enrolment rate in daytime working hours at Rigshospitalet. Hence, recruitment for this study terminates when the last TRAUMOX2 patient is included.

2.4 Statistical interim analysis and stopping guidance

No interim analyses will be conducted for the sub-study, but the TRAUMOX2 trial has a DMSC which conducts a 1st and 2nd interim analysis for the main study. The sub-study will follow the decisions made by the DMSC and steering committee regarding the TRAUMOX2 trial.

2.5 Timing of variables, outcome assessments and final analysis

The registered variables at baseline, during the intervention and during admission (in-hospital) are presented in Tables 1, 2 and 4. In addition to the variables collected during the intervention (Table 2), a figure displaying the median hourly SpO₂ with interquartile ranges for both groups will be made. The primary and secondary outcomes are presented in Table 3. In addition to Table 3, a figure showing each selected biomarker's median values according to randomisation group with interquartile ranges at H_{start} (baseline), H8 (8-10 hours after randomisation), H24 (24 hours after randomisation ± 3 hours) and H48 (48 hours after randomisation ± 3 hours) will be made. The exploratory secondary outcomes (in-hospital variables) at day 30 are presented in Table 4.

3. Statistical principals

3.1 Confidence intervals and P values

We will use a significance level of 5% and thus 95% confidence intervals (CI) on our estimates. Significance tests will be two sided. The secondary outcomes and exploratory secondary outcomes will be adjusted for multiple testing by having their *P*-values assessed using a significance level lower than 5% according to the Benjamini-Hochberg method.³¹ Hence, for the *P*-values of the exploratory secondary outcomes it will be indicated whether they are significant while controlling the false discovery rate at 5%.

3.2 Adherence and protocol deviations

For all TRAUMOX2 trial participants, it is possible to deviate from the protocol if clinically justified by the treating physician. These reasons should always be documented in REDCap.

A major protocol violation will be defined as:

- Restrictive O₂ group, during the intervention period

For non-intubated trial participants: Supplemental oxygen ≥ 3 L O₂/min AND an SpO₂ $\geq 98\%$ recorded at two consecutive hourly time points on the data collection sheet.

For intubated trial participants: FiO₂ > 0.4 AND an SpO₂ $\geq 98\%$ recorded at two consecutive hourly time points on the data collection sheet.

- Liberal O₂ group, during the intervention period

For non-intubated trial participants: Supplemental oxygen < 3 L O₂/min at two consecutive hourly time points on the data collection sheet.

For intubated trial participants: FiO₂ < 0.4 at two consecutive hourly time points on the data collection sheet.

For the main paper, data on protocol deviations and major protocol violations will be presented in Table 2.

3.3 Analysis populations

In the analyses we will exclude patients that:

- Are expected to be discharged within 24 hours after trauma centre admission
- Sustain a major protocol violation during the intervention
- Are discharged from Rigshospitalet or die within 24 hours post-trauma

Please see Figure 1. If consent is withdrawn by a patient, no data after the day of withdrawal will be collected; please see section 4.3 regarding withdrawal and follow-up.

4. Trial population

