Our experiences from TRAUMOX1 reflect the study design of the current trial proposal: TRAUMOX2. In TRAUMOX1 we experienced 24 hours to be slightly excessive to represent only the acute phase post trauma for which reason we will shorten this time-period to eight hours in TRAUMOX2. Furthermore, we found that several physicians had important concerns with the high dosage of oxygen in the liberal arm for which reason the concentration will be reduced. Finally, we did not randomise trauma patients in the pre-hospital phase, but instead on arrival at the trauma bay (median [IQR] time to randomisation: 7 [4-10] minutes, median [IQR] time from trauma to trauma bay arrival: 51 [29.0-67.5] minutes). To limit this inconsistent exposure to oxygen in the pre-hospital phase prior to inclusion we will initiate the intervention in the pre-hospital phase where possible in TRAUMOX2. This is consistent with our hypothesis that a liberal supplemental oxygen strategy may be detrimental and should be avoided as soon as possible. Hence, the study should be initiated in the prehospital setting in alignment with other time critical emergency research studies.

2. Study objectives

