As soon as the trauma team is activated, the including physician (e.g. the trauma leader or an attending anaesthesiologist) judges whether the patient is eligible for the study. If eligible, the including physician will obtain proxy consent through a legally appointed study guardian (physician) i.e. by physical presence or by telephone if needed. In other countries than Denmark, proxy consent might not mandatory before inclusion. National rules and laws will be followed in the specific country on proxy consent and on trial participant/trial participant's next-of-kin consent in general. When the trauma patient is included, the including physician randomises the trial participant to the intervention (restrictive oxygen strategy) or control (liberal oxygen strategy) by opening a concealed envelope with information on allocation. Allocation will be based on trauma centre, and whether the trial participant is intubated at inclusion. The envelope contains a specific study ID number matching the study ID number in the randomisation list. Furthermore, the envelope contains instructions on the allocated intervention regarding inclusion details. The including physician will register the trial participant in a database. In addition, the oxygen treatment and saturation registration form "Data collection sheet" will be part of the envelope in the paper "Randomisation, data collection sheet and REDCap inclusion". Treatment is initiated and continued for eight hours after enrolment. Time of initiation equals T0 (see figure 1) and must not be delayed more than 90 minutes after hospital arrival.

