5.1 Outcome definitions

5.1.1 Primary outcome and secondary outcomes

The primary outcome will be the level of malondialdehyde (MDA) at H24.

The secondary outcomes will be the levels of MDA at H_{start}, H8 and H48, superoxide dismutase (SOD), interleukin-6 (IL-6), interleukin-8 (IL-8), interleukin-10 (IL-10), intercellular adhesion molecule-1 (ICAM-1), vascular endothelial growth factor (VEGF) and granulocyte colony-stimulating factor (G-CSF) at H_{start}, H8, H24 and H48.

The details of all primary and secondary outcomes are presented in Table 3.

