For intubated trial participants: FiO₂ <0.4 at two consecutive hourly time points on the data collection sheet.

TABLE 3 - PRIMARY OUTCOME AND SECONDARY OUTCOMES

Primary outcome	Unit
Malondialdehyde (MDA) at H24	μM (median)
Secondary outcomes	
Malondialdehyde (MDA) at H _{start} , H8 and H48	μM (median)
Superoxid dismutase (SOD) at H _{start} , H8, H24 and H48	ng/mL (median)
Interleukin-6 (IL-6) at H _{start} , H8, H24 and H48	pg/mL (median)
Interleukin-8 (IL-8) at H _{start} , H8, H24 and H48	pg/mL (median)
Interleukin-10 (IL-10) at H _{start} , H8, H24 and H48	pg/mL (median)
Intercellular adhesion molecule-1 (ICAM-1) at H _{start} , H8, H24 and H48	pg/mL (median)
Vascular endothelial growth factor (VEGF) at H _{start} , H8, H24 and H48	pg/mL (median)
Granulocyte colony-stimulating factor (G-CSF) at H _{start} , H8, H24 and H48	pg/mL (median)

H_{start}, H8, H24 and H48 are evaluated at:

H_{start}: Closest possible time from time of randomisation upon arrival to the trauma centre

H8: After the 8-hour intervention has ended and up to 2 hours after

H24: At 24 hours ± 3 hours after time of randomisation

H48: At 48 hours ± 3 hours after time of randomisation

TABLE 4 - EXPLORATORY SECONDARY OUTCOMES (IN-HOSPITAL VARIABLES)

[figure not shown]
Variable	Definition
30-day mortality (y/n)	
Major respiratory complications (pneumonia* and/or ARDS**) within 30 days (y/n)	Assessed by two specialists in anaesthesia, intensive care medicine, emergency medicine or similar using blinded medical records, laboratory and microbiology results, and radiological assessments
Intensive Care Unit admission (y/n)	
Intubation post randomisation (y/n)	During and after intervention
If yes, location, time and date of intubation	Pre-hospital, Trauma Centre, Intensive Care Unit
	Mechanical ventilation initiated as part of general anaesthesia on spontaneously breathing patients to facilitate surgery is not included
Sepsis during hospital admission (y/n)	Clearly stated in the patient's medical record by a physician or assigned as a diagnosis

*Pneumonia is categorised as non-ventilator-associated pneumonia (PNEU) or ventilator-associated pneumonia (VAP), defined by the CDC criteria³⁴

**ARDS is categorised as mild, moderate, or severe, defined by the Berlin definition³⁵

Figures

CONSORT flow diagram of screening, inclusion and follow-up

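### The 24-hour post-trauma exclusion runs on a different clock from the blood samples, so it can discard valid early H24 values and discards valid H_start and H8 values

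*SAP*

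**What the plan says.** SAP section 3.3 lists three exclusions that apply to the analyses without distinction of time point. The third removes patients who "Are discharged from Rigshospitalet or die within 24 hours post-trauma", so its clock starts at trauma. The first removes patients who "Are expected to be discharged within 24 hours after trauma centre admission", so its clock starts at admission.

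The outcome uses a third origin. SAP section 5.1.1 states: "The primary outcome will be the level of malondialdehyde (MDA) at H24". SAP section 2.5 gives the timing as "H24 (24 hours after randomisation ± 3 hours", and the footnote to SAP Table 3 agrees: "H24: At 24 hours ± 3 hours after time of randomisation". H8 is drawn 8 to 10 hours after randomisation. MDA at H_start, H8 and H48, and the other biomarkers at all four time points, are secondary outcomes.

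Nothing in the readable text makes the third exclusion depend on whether a sample was obtained, or keeps a patient who already has one.

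**The concern.** A rule that decides who enters the H24 comparison should separate patients who could be measured from those who could not. This one uses discharge or death on a clock that differs from the sampling clock by each patient's trauma-to-randomisation time. A patient sampled at 21.5 hours after randomisation and discharged at 22.5 hours has a valid primary value but, at the pilot's typical timings, is excluded.

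The same bullet reaches back to earlier samples. A patient with valid H_start and H8 values who leaves at 15 hours is absent from the H_start and H8 comparisons as well, although nothing is missing there.

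Discharge and death happen after randomisation. Excluding measured patients because of them loses information and allows selection that randomisation does not protect against. The weighting in SAP section 5.3 is for missing outcomes; it is not described as restoring patients removed by rule. By SAP section 6, 88 patients had been included against the estimated 120, with one week of recruitment left, so avoidable losses are unwelcome.

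**Working it through.** **Inputs**
- Exclusion cut: 24 h after trauma (SAP 3.3).
- H24 window: 24 ± 3 h, that is 21 to 27 h after randomisation (SAP 2.5 and Table 3).
- H8 draw: 8 to 10 h after randomisation (SAP 2.5).
- Pilot timings (Protocol section 1): "median [IQR] time from trauma to trauma bay arrival: 51 [29.0-67.5] minutes" and "median [IQR] time to randomisation: 7 [4-10] minutes".
- Latest trauma-bay start (Protocol 3.4): "must not be delayed more than 90 minutes after hospital arrival".

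**Where the cut falls at H24.** Let L be the time from trauma to randomisation, in hours. On the randomisation clock the cut is at 24 − L. It lies inside 21 to 27 h when L < 3. The part of the window before the cut lasts 3 − L hours. Adding medians or quartiles only approximates the distribution of L.

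| L | Cut after randomisation | Window before the cut |
|---|---|---|
| 29 + 4 = 33 min (0.55 h) | 23.45 h | 2.45 h |
| 51 + 7 = 58 min (0.97 h) | 23.03 h | 2.03 h |
| 67.5 + 10 = 77.5 min (1.29 h) | 22.71 h | 1.71 h |
| 51 + 90 = 141 min (2.35 h) | 21.65 h | 0.65 h |
| 180 min (3 h) | 21.00 h | 0 |

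The pilot randomised on arrival at the trauma bay. Prehospital inclusion shortens L and moves the overlap towards 3 h.

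**What must happen for an H24 value to be lost.** All three conditions are needed: L < 3 h; the sample is drawn before the cut (the first 2 h or so of the window at L = 58 min); and the patient leaves or dies after the draw but before the cut. A sample at the nominal 24 h is taken 24 + 0.97 = about 25 h after trauma, so this rule cannot discard it.

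The frequency depends on sampling practice, which the documents do not describe. As an assumption only: let sampling times be normal around 24 h with SD 1 h, leaving times uniform over the window, and L = 0.97 h. Then about 1.5% of patients who leave inside the window would be measured and then excluded. If 10% to 20% of 88 left inside the window (also assumed), that is 8.8 to 17.6 leavers, and 0.015 × 8.8 to 0.015 × 17.6 = 0.13 to 0.26 patients. Routine sampling early in the window would give more.

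**H_start, H8 and H48.** At L = 58 min, an H8 sample is followed by 23.03 − 10 = 13.0 h to 23.03 − 8 = 15.0 h in which discharge or death removes a valid H8 value and the H_start value with it. The corresponding span at H24 is at most 2.03 h and needs an early draw. For patients who leave before eight hours, the requirement in SAP 2.1 to complete the intervention may exclude them anyway, so the clear case starts at the H8 draw. H48 is not affected: a patient gone before the cut has no H48 sample.

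**Power, for scale.** The SAP's figure reproduces. Normal approximation for means, two-sided 5%, difference 2 µM, SD 3 µM: n per arm = 2 × (1.960 + 1.282)² × 3² / 2² = 47.3, so 48. With 120 less 5% = 114, or 57 per arm, power = Φ(2 / (3√(2/57)) − 1.96) = Φ(1.60) = 94.5%. Losing 1%, 2% or 5% of the 114 values (assumed) gives 94.3%, 94.1% or 93.4%. The planned analysis compares medians, so these figures show only the size of the change.

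**The case against.** The strongest reply is that the mismatch is real but almost empty at the primary time point. Sampling near the nominal 24 hours loses nothing, Protocol 3.2 requires an expected stay of at least 24 hours at inclusion, and the change in nominal power is slight. Figure 1 of the SAP is not shown and the sub-study protocol is not among the documents, so operational details may already deal with some cases. All of this stands as a limit on size. It does not answer the H_start and H8 losses, which need no early H24 draw, and no readable text repairs the rule.

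The mismatch also works in the other direction. A patient who leaves after 24 hours post-trauma but before the H24 draw stays in the analysis set with no primary value. A reader might call that a second error. It is not one in itself: SAP 5.3 assigns missing outcomes to inverse probability weighting, and its remark that these are mainly withdrawals does not limit it to them. What is missing is a statement that it covers this case.

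A reader might also conclude that the first exclusion should go because it uses yet another clock. The documents do not support that. It rests on expected stay and closely follows the main trial's criterion in Protocol 3.3, so it can remain as an eligibility rule.

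**Conclusion.** The point holds as a defect in the stated analysis set: the third exclusion in SAP 3.3 removes measured patients because of a later event. For L < 3 h, which the pilot timings suggest is typical, it can discard a valid early H24 MDA value. It also discards valid H_start and H8 values, and most of the avoidable loss is likely there.

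The size cannot be stated from the documents, which give no discharge or death times and no sampling practice. The H24 loss may be few or none. It would be tempting to infer that the rule costs a material number of primary values, or shifts the primary comparison by some fixed amount. Neither is supported. A larger count requires assuming that nearly everyone who leaves before the cut was sampled as the window opened. A bias figure based on cutting unequal shares of mild cases from the two arms would describe the exclusion of early leavers as a whole, most of which remains under any sample-based rule. Nor do the documents show that discharge timing depends on arm.

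The change is worth making before database export because it is specific and cheap and removes avoidable selection. The conclusion rests on reading section 3.3 as written and on the pilot timings applying roughly to this sub-study.

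**What to change.** Replace the third exclusion in SAP 3.3 with text such as: *Each time-point comparison (H_start, H8, H24, H48) includes every otherwise eligible sub-study patient with a sample taken in that time point's window, measured from randomisation, whatever the later discharge or death. Patients who leave or die before a sample is drawn are reported in Figure 1 by arm and reason.*

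In SAP 5.3, state whether the weighting applies to patients discharged alive without a sample. Deaths before a draw need separate mention, because no later level exists to be recovered. Keep the first exclusion as the eligibility rule. The Table 4 outcomes need no sample, so state which set they use once the third exclusion is gone.

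The cost is a sentence or two before export. Two consequences follow. The analysed number will differ by time point and must be shown in the flow diagram. Actual sample times must also be available: SAP Table 2 lists only the delay from randomisation to the baseline sample, and Protocol 3.7 lists date of death and lengths of stay, so confirm that the H8, H24 and H48 draw times are in the database.
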